11 ADVERSE EVENTS

Potential risks to the patients are listed in the Clinical Risk/Benefit Analysis Section (see Appendix 1- Clinical Risk/Benefit Analysis).

Patients will be carefully monitored during the study for possible adverse events (AEs). During each clinical follow-up visit, the investigator or designee will determine AE occurrences. Each adverse event is considered to be either anticipated or unanticipated as described below. The site is required to report all adverse events that occur during the study. The investigator will classify the AEs based on the definitions as follows:

11.1 General Adverse Event Definitions

Adverse event: is defined as any untoward medical occurrence, unintended disease or injury, or untoward clinical signs (including abnormal laboratory findings) in patients, users, or other persons, whether or not related to the investigational medical device.

An adverse event can be further identified by a condition as noted below:

- a) A unique symptom or event that is a change from the patient's baseline status
- b) A series of symptoms or events that can be categorized as a single entity based on definitions found herein
- c) A specific diagnosis responsible for a clinical change
- d) A worsening or exacerbation of a pre-existing condition

11.2 Serious Adverse Events

A serious adverse event (SAE) is an adverse event that:

• Results in death

PROTOCOL NUMBER: 2017-05

- Is life-threatening
- Requires inpatient hospitalization or prolongation of existing hospitalization
- Results in persistent or significant disability/incapacity, or
- Is an important medical event which may jeopardize the patient, and may require medical or surgical intervention to prevent one of the above outcomes

11.2.1 Unanticipated Adverse Device Effect

Unanticipated adverse device effect (UADE) is defined in accordance with 21 Code of Federal Regulations (CFR) Part 812.3 as any serious adverse effect on health or safety or any life-threatening problem or death caused by, or associated with, a device, if that effect, problem, or death was not previously identified in nature, severity, or degree of incidence in the investigational plan or application (including a supplementary plan or application), or any other unanticipated serious problem associated with a device that relates to the rights, safety, or welfare of subjects.

11.3 Adverse Event Assessment

Adverse events in an implanted patient will be assessed by the Investigator for causality to the investigational device or index procedure.

Investigational Device Related Adverse Event: An adverse event, which in the judgment of the Investigator, results from use of the Edwards Cardioband System.

Procedure Related Adverse Event: An adverse event which, in the judgment of the Investigator, results as a consequence of the index (i.e. Edwards Cardioband System) procedure.

11.4 Events Expected to Occur with Edwards Cardioband System Index-Procedure

For purposes of this study, the following events are not considered reportable adverse events because they are normally expected to occur in conjunction with treatment of mitral regurgitation or structural heart interventional procedures, or are associated with customary, standard care of patients undergoing minimally invasive cardiovascular intervention:

- Chest pain without associated enzyme/ECG changes.
- Post-procedure pain (within 48 hour of procedure and treated with non-opioids).
- Post-anesthesia emesis, nausea, or headache (within 48 hours of procedure).

- PROTOCOL NUMBER: 2017-05
- Electrolyte imbalance without clinical sequelae and not requiring correction following the index procedure.
- Pre Planned future Surgical Procedures.
- Low grade temperature increase (≤ 101°F or 38.5°C) without signs of infection.
- Dizziness: Imprecise term commonly used to describe various symptoms such as faintness, giddiness, imbalance, lightheadedness, unsteadiness or vertigo (in the initial 48 hours post procedure).
- Elevated White Blood Count, outside the standard laboratory normal value, without signs and symptoms of infection.
- Minor, localized tenderness, swelling, induration, oozing, etc. at access site(s).
- Sinus bradycardia/tachycardia that does not require treatment or intervention.
- Systolic or diastolic blood pressure changes that do not require treatment or intervention.
- Hyperglycemia: the use of insulin in a diabetic patient in the post op period.
- Non-clinically significant lab variances.
- Non-clinically significant events.

This listing of events is intended to provide guidance to the investigational sites for the purpose of adverse event reporting. The Investigator at the investigational site should utilize his/her own clinical judgment in evaluating adverse experiences, and may decide that the above events should be reported as adverse events.

11.5 Adverse Event Reporting Requirements

11.5.1 General Reporting Requirements (All Adverse Events)

All adverse events (i.e. serious or non-serious, anticipated or unanticipated) must be recorded on the Adverse Event eCRF by the investigator (or designee) and all device deficiencies must be reported to the Sponsor, with the exception of those adverse events identified in Section 11.4. The report should include: start date of the adverse event, treatment, resolution, and assessment of both the seriousness and the relationship to the investigational device and the procedure.

The following principles must also be adhered to by the Investigator:

- PROTOCOL NUMBER: 2017-05
 - Completion of separate Adverse Event forms to document each event
 - Completion of separate forms for each device observation/ deficiency
 - The forms must be electronically signed by the Investigator, and
 - Additional information related to adverse events as requested by the Sponsor
 - It is the responsibility of the Investigator to inform their IRB/EC of serious adverse events as required by their IRB/EC procedures and in conformance with applicable regulatory requirements.

In the event of a suspected device observation or deficiency, the device shall be returned to Sponsor for analysis. Instructions for returning the investigational device will be provided by the Sponsor.

11.5.2 Reporting Requirements (Non-Serious Adverse Events)

All non-serious adverse events should be reported by the Investigator (or designee) by submitting the Adverse Event eCRF to the Sponsor within 7 calendar days of learning of the adverse event, or at the Sponsor's request. In the event that the electronic system is not available, the event should be reported by email to TMTT [contact] with the following minimum information:

- Study site number
- Patient ID number
- Date of event
- Site's awareness date
- Adverse event description
- Causal relationship to the device and Implant procedure

The AE eCRF should be submitted as soon as possible thereafter.

11.5.3 Reporting Requirements (Serious Adverse Events)

All serious adverse events should be reported by the Investigator (or designee) by submitting the Adverse Event eCRF to the Sponsor, within 3 calendar days of learning of the adverse event.

In the event that the electronic system is not available, the event should be reported as noted above in section 11.5.2.

The Investigator (or designee) shall provide source documents related to the serious and/or unanticipated adverse event as requested by Sponsor or their designee. Furthermore, the Investigator shall report the event to the IRB/EC in accordance with local/institutional requirements. The Sponsor will evaluate all serious adverse events for reportability as an unanticipated adverse device effect in accordance with 21 CFR Part 812.46(b)3. The investigator and Sponsor will comply with reporting requirements per 21 CFR Part 812.150. A Sponsor who conducts an evaluation of an unanticipated adverse device effect under 812.46(b) shall report the results of such evaluation to FDA and to all reviewing IRB's/EC's and participating investigators within 10 working days after the Sponsor first receives notice of the event. Thereafter the Sponsor shall submit additional reports concerning the event as FDA requests.

Finally, the Investigator should follow all unresolved serious adverse events until the events are resolved, the patient is lost to follow-up, the patient has withdrawn consent, or the adverse event is otherwise explained.

11.6 Patient Death

Patient death during the investigation should be reported to Sponsor or designee within 3 calendar days of Investigator's knowledge of the death. The Adverse Event that resulted in death should be entered in the database on the Adverse Event form within 3 calendar days and include a brief description of the relevant details of the death. The electronic Adverse Event eCRF must be electronically signed by the Investigator. A copy of the death records, death certificate and an autopsy report (if performed) should be sent to the Sponsor as soon as possible or designee within 10 days following the death. In addition, patient death must be reported to the IRB/EC in accordance with IRB/EC requirements.

³ Unanticipated adverse device effect is any serious adverse effect on health or safety, any lifethreatening problem or death caused by, or associated with a device, if that effect, problem, or death was not previously identified in nature, severity, or degree of incidence in the application; or any other unanticipated serious problem associated with a device that relates to the rights, safety, or welfare of patients.

11.7 Treatment Failures & Device Malfunctions

All suspected device deficiencies, malfunctions or failures of the Edwards Cardioband System should be documented on the appropriate eCRF. In the event of a suspected deficiency or other device issue, the device shall be returned to the Sponsor to the extent possible for analysis. Instructions for returning the investigational device will be provided by the Sponsor. F

11.8 Sponsor Reporting

A summary of adverse events will be reported to the applicable regulatory authority at least annually, or as required per applicable regulatory authority.

Sponsor or their designee is responsible for the classification and reporting of adverse events and ongoing safety evaluation of the clinical investigation in accordance with and the relevant regulatory requirements, as applicable.

12 Patient Withdrawal / Discontinuation

12.1 Patient Withdrawal/ Discontinuation/ Premature Study Termination

Once the patient has been enrolled in the study, he/she may withdraw his/her consent to participate in the study at any time without jeopardy or prejudice. Participation in this clinical investigation is entirely voluntary. Likewise, there may be a reason identified by the Investigator that deems the patient no longer suitable for the study. In either case, the Investigator should contact the study Sponsor, or its designee, to discuss the circumstances for discontinuation/withdrawal. Reasons for discontinuation or withdrawal may include, but are not limited to the following:

- The Investigator feels that the patient can no longer fully comply with the requirements of the study or if any of the study procedures would not be in the best interest of the patient.
- The patient is lost to follow-up. A patient will be considered "lost to follow-up" and terminated from the study when all of the following criteria have been met:
 - Failure to complete the remainder of the scheduled study visits without due cause; and
 - Documentation of three unsuccessful attempts to contact the patient via phone/email and/or registered mail.

PROTOCOL NUMBER: 2017-05

- The patient withdraws their consent for participation in the study.
- The patient incorrectly randomized in the study and treatment has not been initiated; or
- The Sponsor prematurely terminates the study. Circumstances under which the Sponsor can suspend or stop this trial include, but are not limited to, low study enrollment or new information regarding safety or efficacy.

12.2 Data Collection & Follow-Up for Discontinued/Withdrawn Patients

All randomized patients are considered eligible for the assigned treatment and protocol defined follow-up and will be required to adhere to the assessment schedule outlined in Table 4. Patients may withdraw at any time from the clinical study without jeopardy or prejudice. If a patient terminates from the study, the reason for study termination will be recorded. If termination is a result of an adverse event or death, an Adverse Event eCRF will also be completed. Patients who withdraw consent after treatment will not be required to undergo follow-up after withdrawal, but will still be considered part of the patient cohort.

Every attempt will be made to conduct an exit/final visit prior to a patient terminating from the study. The reason for early discontinuation/termination will be documented in the source documents and eCRFs.

12.3 Patients Lost to Follow-Up

All reasonable efforts (at least 3 contact attempts via phone/email and/or 2 registered letters) will be made to obtain complete data for all patients, before they are considered lost to follow-up. When possible, Social Security files and the National Death Index should be consulted in an attempt to ascertain mortality status for losses to follow-up. Missing observations may occur due to patients who are lost to follow-up, or demonstrate noncompliance with the required assessments.

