6.7 Technical Feasibility Assessment of Edwards Cardioband System Implantation by **Sponsor**

The Sponsor will review applicable patient data collected at Screening and Baseline Visits (e.g. cardiac CT) to determine the technical feasibility of implanting the Edwards Cardioband System. The Sponsor may also assist the site in determining the most appropriate implant size for the patient.

Central Screening Committee Determination

After the Central Screening Committee (CSC) has reviewed all screening and baseline assessments and reached a decision on eligibility, the decision will be communicated to the site. The site will proceed to scheduling the case for approved patients in accordance with institutional procedures.

^{*}If TTE is more than 60 days from the procedure, a repeat TTE will be required.

Randomization Procedure 7

Patients will be prospectively randomized into the clinical study. Randomization will occur only after the patient provides informed consent, completes all required screening and baseline procedures, and satisfies the study eligibility criteria (including eligibility determination by the Central Screening Committee). Randomization shall be performed after cases have received final approval from the CSC and Sponsor and the case has been scheduled at the institution.

Eligible patients will be randomly assigned in a two to one (2:1) ratio to either treatment with Edwards Cardioband System + Guideline Directed Medical Therapy (Device Group) versus Guideline Directed Medical Therapy alone (Control Group).

Randomization assignment will be generated via the randomization module of the EDC system. Randomization scheme will be based on random blocks and will be stratified by:

- study center
- baseline ischemic vs. non-ischemic disease

This randomization schedule (list) will be masked to study patients, site personnel, study team and Sponsor. Only the un-blinded statistician and designates will be privy to the masked randomization scheme.

A patient is not considered randomized until the randomization assignment has been dispensed. If at any time after randomization a patient becomes ineligible or withdraws, the patient is still considered randomized.

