13.3.2 Intent-to-Treat (ITT) Population – for safety analysis

The Intent-to-Treat population (ITT) [full analysis set (FAS)] will consist of all patients who have signed informed consent and have been randomized.

Patients that have entered the procedure room but have not received an implant attempt (passing of any Edwards Cardioband System component past the skin) will be deregistered and followed through 30 days for safety purposes only.

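### The death-record check covers only losses to follow-up, so 1-year vital status is not planned after consent withdrawal and not specified after investigator discontinuation

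*Protocol*

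**What the plan says.** Protocol 12.1 lists the ways a patient can leave. Loss to follow-up has its own bullet and criteria. Withdrawal of consent is another. A third is discontinuation by the investigator, for example: "The Investigator feels that the patient can no longer fully comply with the requirements of the study". Section 12.1 says nothing about contact after that third kind of exit.

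Protocol 12.2 sets the default: "All randomized patients are considered eligible for the assigned treatment and protocol defined follow-up and will be required to adhere to the assessment schedule". It waives follow-up in one case: "Patients who withdraw consent after treatment will not be required to undergo follow-up after withdrawal, but will still be considered part of the patient cohort". At exit it adds: "Every attempt will be made to conduct an exit/final visit prior to a patient terminating from the study". Protocol 7 states: "If at any time after randomization a patient becomes ineligible or withdraws, the patient is still considered randomized". The record search in Protocol 12.3 is then aimed at one exit route: "When possible, Social Security files and the National Death Index should be consulted in an attempt to ascertain mortality status for losses to follow-up".

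Device patients who enter the procedure room but get no implant attempt "will be deregistered and followed through 30 days for safety purposes only" (Protocol 13.3.2; SAP 4.2 agrees).

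On the analysis side, time to all-cause death is the first component of co-primary endpoint II. Under Protocol 13.4.2 and SAP 8.2, a pair with a censored member is judged on the shorter of the two follow-up times. SAP 5.1 includes study termination among the dates that define last information, and uses that date for censoring in survival analyses.

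**The concern.** Death decides Finkelstein-Schoenfeld (FS) pairs before anything else. Cardiovascular and all-cause mortality are also hierarchically tested secondary endpoints (Protocol 13.4.4, SAP 8.4). A death can be found from public records without any visit, so it is the component that is easiest to complete after a patient leaves. The plan uses that option for one exit route only.

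Patients know their arm: a Control patient is told that the scheduled case is cancelled (Protocol 4, SAP 2.3). Reasons for leaving could therefore differ between arms. If they do, and if leaving is linked to prognosis, the deaths that go unseen are unequal by arm and the comparison at step 1 is biased. Later modelling can test how much this matters, but it cannot observe the deaths.

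**Working it through.** **Step 1. Exit routes side by side**

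| Exit route | Follow-up after exit | Named in 12.3 check | In mITT |
|---|---|---|---|
| Lost to follow-up | Contact attempts, then records | Yes, when possible | Yes, if Control or implanted |
| Consent withdrawn after treatment | Waived (12.2) | No | Yes, if Control or implanted |
| Discontinued by investigator | Not specified; 12.2 default schedule pulls the other way | No | Yes, if Control or implanted |
| Deregistered (Device, no implant attempt) | 30 days, safety | No | No (13.3.3, SAP 4.3) |

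The gap that reaches co-primary endpoint II is in rows two and three. Deaths before exit are reported (Protocol 11.6, 12.2).

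**Step 2. The plan's own power figure**

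The inputs come from the Synopsis, Protocol 13.5 and SAP 8.11: 300 evaluable patients at 2:1 (200 and 100), two-sided alpha 0.05, 1-year mortality 20% in both arms, the stated distributions of heart failure hospitalizations, and responder rates of 50% versus 10% for both the walk test and KCCQ. The test uses T and V from SAP 8.2 with the all-cause hierarchy of Protocol 13.4.2. With independent components and 5,000 simulated trials, power is 93.1%, which agrees with the Synopsis (above 90%). If the walk-test and KCCQ responders are the same patients, power is 76.2%. The 87% in Protocol 13.5 and SAP 8.11 lies between the two.

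**Step 3. How many deaths could go unseen**

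- Attrition allowed: 0.20 × 375 = 75 patients. Expected deaths: 0.20 × 375 = 75.
- Constant hazard: λ = −ln(0.8) = 0.223 per year.
- For exit time u uniform on the year, the chance of dying after u but within the year is exp(−λu) − 0.8. Its mean is (1 − 0.8)/0.223 − 0.8 = 0.8963 − 0.8 = 0.0963.
- All leavers: 75 × 0.0963 = 7.2 deaths. This includes losses to follow-up, which 12.3 already covers.
- Half of leavers by the uncovered routes (assumed): 37.5 × 0.0963 = 3.6, about 4 of 75 (4.8%).
- Conditioning on being alive at exit gives 1 − 0.8963 = 0.1037 and 37.5 × 0.1037 = 3.9, again about 4.

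A simulation with 10% random withdrawal in each arm also gives 3.6 unseen deaths.

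**Step 4. What the loss does to the FS test**

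These runs use N = 375 (250 Device, 125 Control) and 2,000 to 4,000 simulated trials each. All withdrawal patterns are assumptions.

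*Random withdrawal, same rate in both arms, design effect true:*

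| Withdrawal | Unseen deaths | Power, deaths unknown | Power, deaths known |
|---|---|---|---|
| 5% | 1.8 | 96% | 96% |
| 10% | 3.6 | 95% | 91% |
| 20% | 7.3 | 86% | 82% |

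Knowing the deaths does not raise power here, because the plan assumes equal mortality and step 1 then adds only noise.

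*No true effect, deaths hidden by withdrawal (Device deaths expected: 0.20 × 250 = 50):*

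| Hidden, Device / Control | Device deaths hidden | False positives favoring Device | Same, deaths known |
|---|---|---|---|
| 10% / 0% | 5 | 4.7% | 2.6% |
| 25% / 0% | 12.5 | 11.4% | 2.5% |
| 50% / 0% | 25 | 32.9% | 2.4% |
| 25% / 25% | 12.5 | 2.5% | 2.8% |

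The nominal value is 2.5%. The simulation standard error at 11.4% is √(0.114 × 0.886/4000) = 0.5 points. In the other direction, with the design effect true, hiding 25% or 50% of Control deaths only gives power of 91% or 73%.

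**Step 5. How extreme these scenarios are**

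Under the step 3 split, 10% of 250 = 25 Device patients leave by the uncovered routes, and average mortality gives 25 × 0.0963 = 2.4 unseen Device deaths. Hiding 5 needs about twice that risk (5/25 = 20%). Hiding 12.5 needs half of those 25 to die within the year.

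**The case against.** Several provisions soften the gap. Protocol 12.2 keeps randomized patients on the schedule unless consent is withdrawn. Protocol 10 allows testing by a local physician when the patient cannot or will not return, and leaves the investigator responsible for obtaining the information. Protocol 11.5.3 follows unresolved serious events and does not make investigator discontinuation a stopping point. Protocol 12.3 asks for reasonable efforts at complete data for everyone. Controls may be offered the device after completing the 1-year assessment (Protocol 9), which gives them a reason to stay. All of this stands, but none of it provides a 1-year vital-status check after withdrawal or discontinuation.

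Protocol 13.6 also promises multiple imputation and tipping-point analyses. These would test the influence of unknown deaths without finding them. SAP 6.2 specifies no such analysis; that is a separate point to reconcile.

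A reader might infer more than the documents support:

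- *That deaths of deregistered Device patients are missed in co-primary endpoint II through the record check.* They are outside the mITT by definition, so no record search would bring them in.
- *That investigator-discontinued patients get no further contact.* The text is silent on this, and the 12.2 default points the other way.
- *That the wording about treatment in 12.2 leaves Controls in a gap of their own.* Section 8 counts GDMT as treatment; if Controls were not covered, the default schedule would apply to them.
- *That the sickest patients leave, or that about 10% of step 1 deaths are lost.* No data on who withdraws are given, and the 7 of 75 behind that share includes losses to follow-up that 12.3 covers.

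**Conclusion.** The point holds in a limited form. For mITT patients who withdraw consent, no 1-year vital status is planned; for those discontinued by the investigator, none is specified. Both are censored at exit, so their later deaths do not count at FS step 1 or in the two mortality tests.

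The expected number is small: about 4 of some 75 deaths, if half of the allowed attrition goes by these routes with uniform exit times and average mortality. Loss that follows the same pattern in both arms neither inflates type I error nor costs power relative to knowing the deaths. The risk lies in unequal loss. Under the null, hiding 10% or 25% of Device deaths and no Control deaths gives about 5% or 11% false positives favoring Device, against 2.5%. The 25% case needs leavers with far worse than average survival. The documents neither support nor exclude such a split. It is plausible when patients know their arm, and the remedy is cheap, so the sponsor should make the change.

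**What to change.** - In Protocol 12.3, extend the death-record check to every randomized patient whose 1-year vital status is unknown, whatever the exit route, subject to consent and local law. Name equivalent sources outside the US: both named sources are US ones, and the Synopsis allows up to 50% of enrollees from Europe.
- In Protocol 12.1 and 12.2, state that investigator-discontinued patients remain under phone or record contact for vital status and heart failure hospitalization through 1 year, unless they refuse that too.
- In the SAP, use deaths found for mITT patients in FS step 1 and in the mortality tests, and report vital-status completeness by arm.
- For deregistered patients, use vital status for ITT reporting only. Their absence from co-primary endpoint II is a separate mITT-versus-ITT question.

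The cost is a change to protocol and consent wording, plus calls and record searches for a few dozen patients at most, with no added visits or procedures. Some countries may not allow the search. The change should be made prospectively, since consent for later record checks is hard to obtain once a patient has left.
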